6.9.3.2. Electrical Impedance Myography (EIM, Optional)

EIM measures the electrical impedance of individual muscles as a representation for muscle composition, which changes with disease progression. Using a single probe that contains both stimulating and recording electrodes, measurements are taken twice over each muscle. The probe is placed against a clean area of skin for less than 10 seconds per recording. Four muscles will be tested in upper and lower extremities; elbow flexors, wrist extensors, knee extensors, and ankle dorsiflexors, for a total of 8 muscles tested per subject. The minute electrical signals produced by the stimulator are imperceptible; subjects only notice the pressure of the probe against their skin. Sites will have the option of collecting the EIM outcome data.

6.9.3.3. Analysis of Cerebrospinal Fluid

Few studies have been performed that assess and quantify the presence of neurotrophic factors in the CSF. Since MSC-NTF secrete several known neurotrophic factors, we intend to develop ELISA assays for neurotrophic factors and use these assays to assess the concentration of these factors after treatment. We are also exploring the possible assessment of several putative ALS biomarkers in these CSF samples.

6.9.4. Statistical Methods and Sample Size Determination

Summaries for continuous variables will include the sample size, mean, standard deviation, median, minimum, and maximum. Minima and maxima will be reported with the same precision as the raw values; means, standard deviations, and medians will be presented to one additional decimal place than reported in the raw values. Summaries for discrete variables will include frequencies and percentages. All percentages will be rounded to one decimal place (i.e., XX.X%). Differences between treatment groups will be calculated as MSC-NTF cells – placebo and change from baseline will be calculated as post-treatment – pre-treatment (OR follow-up visit – baseline: e.g. Week 2 – baseline, Week 4 – baseline). The baseline visit will be defined as the last non-missing measure prior to initiation of investigational treatment. Additionally, for the pre-transplantation period and transplantation visits, change from screening (V1) summaries will be calculated as pre-transplantation period/transplantation visit – screening.

All efficacy analyses will use one-sided alpha = 0.10 tests and present one-sided 90% lower confidence limits and two-sided 95% confidence intervals around the difference between treatments as well as two-sided 95% confidence intervals around the point estimates within each treatment group. All summaries will be presented by treatment group.

A statistical analysis plan (SAP) will be prepared and finalized prior to database lock, unblinding and analysis of study results.

6.9.4.1. Analysis Population

The safety population includes all randomized subjects who receive study treatment (treatment or placebo) including those who do not complete the study. The safety population will be analyzed as treated and will be used for the safety analysis.

The full analysis set (FAS) population includes all randomized subjects. The FAS will be analyzed as randomized. Analyses on the FAS population will be considered secondary.

The modified FAS (mFAS) population includes all FAS participants who receive study treatment. The mFAS will be analyzed as randomized. Analyses on the mFAS population will be considered primary.

The per protocol (PP) data set will include all mFAS subjects who have no major protocol violations likely to seriously affect the primary outcome of the study as judged by a blinded evaluation performed by a group of study personnel including the medical monitor, statistician, and clinical project manager prior to the unblinding of the study treatment. Analyses on the PP data set will group subjects according to the treatment actually received. Analyses on the PP population will be considered secondary.

Partially treated subjects will be included in the intention to treat analyses but won't be included in the per protocol analyses.

6.9.4.2. Safety analyses

Primary Objective: The safety of MSC-NTF transplantation via combined IT and IM injection in participants with ALS is the primary objective of this study. Safety endpoints include AEs, changes in physical and neurological examination findings, hematology, serum chemistry, urinalysis, vital signs, and requirement of concomitant medications.

All AEs will be coded to System Organ Class (SOC) and Preferred Term (PT) using the MedDRA®. The number of Treatment-Emergent Adverse Events (TEAEs) and the number of subjects with any TEAEs (along with percentages) will be tabulated by SOC and PT within each SOC by treatment group and over treatment groups. To count the number of subjects with any TEAEs, a subject who experiences multiple TEAEs within the same SOC will be counted only once for that SOC (whether or not the TEAEs are coded to the same PT). A subject who experiences multiple TEAEs coded to the same PT within the same SOC will be counted only once for that particular PT. In the summary, SOC will be listed in ascending alphabetical order; PTs will be listed in order of descending frequency for all subjects within each SOC.

Separate summaries will be provided for the following categories of AEs:

- TEAEs
- TEAEs by severity
- Treatment-related TEAEs
- Serious TEAEs

The proportion of subjects having each AE will be compared between treatment using Fisher's exact tests.

When evaluating changes in safety parameters, baseline will be defined as the last measurement prior to transplantation (i.e., prior to treatment).

Physical examination, neurological examination, hematology, serum chemistry, vital signs and concomitant medications will be summarized using descriptive statistics (n, mean, standard deviation, median, minimum, and maximum) if the data is continuous and using counts and percentages if the data is discrete. Shifts from baseline in categorization of results (e.g. normal/abnormal or low/normal/high) will also be summarized.

6.9.4.3. Efficacy Analyses

Secondary Objectives: The change in slope between the treatment and placebo group and from pre-transplantation to post-transplantation in ALSFRS-R and in SVC (as a percent of normal for age and sex) will be estimated using the mixed linear statistical model.

The fixed effect variables in the model will be:

- Visit, expressed in days from the beginning of treatment (i.e. pre-treatment times will have negative values, post-treatment times positive values).
- Treatment
- Two-way interactions between visit & post-treatment indicator, (0 for pre-treatment visits, 1 for post-treatment visits) and visit & treatment
- Three-way interaction between visit & post-treatment visit indicator & treatment
- Site

The repeated measures within a subject over visit will also be accounted for in the model, wherein, the covariance structure will be evaluated using Bayesian information criterion (BIC). Covariance structures to be evaluated are: unstructured, toeplitz, spatial power with day, and compound symmetry.

The three-way interaction between visit & post-treatment visit indicator & treatment will be used to compare the change in slope in the treatment group to the change in slope in the placebo group.

The post-pre slope estimate within each treatment group will be used to test the change from pre-transplantation to post-transplantation.

Repeated measures covariance will be estimated by restricted maximum likelihood. The Kenward and Roger method will be used to determine degrees of freedom and compute p-values.

Secondary objectives will be evaluated for the FAS, as well as the PP populations.

Exploratory Objectives: The analysis for EIM (optional) and HHD will employ the same modeling approach as described above for the secondary objectives. The analysis for HHD will be based on a combined score reflecting muscles in the right arm.

A further analysis of HHD will compare the score for the right arm to the score for the left arm. The linear mixed model will include, in addition to the terms described above, an indicator for "right arm", interactions between that indicator and all other variables in the model, and a random effect term for the right arm indicator. Therefore, the fixed effect variables in the model will be:

- Visit, expressed in days from the beginning of treatment (i.e. pre-treatment times will have negative values, post-treatment times positive values);
- Treatment;
- Right arm indicator;
- Two-way interactions between visit & post-treatment indicator (0 for pre-treatment visits, 1 for post-treatment visits), visit & treatment, visit & right arm indicator, and treatment & right arm indicator;
- Three-way interactions between visit & post-treatment visit indicator & treatment, visit & post-treatment indicator & right arm indicator, and visit & treatment & right arm indicator;
- Four-way interaction between visit & post-treatment visit indicator & treatment & right arm indicator;

- Site.

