Efficacy	
All efficacy analyses will use one-sided alpha = 0.10 tests and present one-sided 90% lower confidence limits and two-sided 95% confidence intervals around the difference between treatments as well as two-sided 95% confidence intervals around the point estimates within each treatment group. All summaries will be presented by treatment group.
 
Secondary Objectives: The change in slope from pre-transplantation to post-transplantation in ALSFRS-R and in SVC (as a percent of normal for age and sex) will be estimated using the mixed linear statistical model. The fixed effect variables in the model will be:
 
 • Visit, expressed in days from the beginning of treatment (i.e. pre-treatment times will have negative values, post-treatment times positive values); • Treatment; • Two-way interactions between visit & post-treatment indicator, (0 for pre-treatment visits, 1 for post-treatment visits) and visit & treatment; • Three-way interaction between visit & post-treatment visit indicator & treatment; • Site. 
The repeated measures within a subject over visit will also be accounted for in the model, wherein the covariance structure will be evaluated using Bayesian information criterion (BIC). Covariance structures to be evaluated are: unstructured, toeplitz, spatial power with day, and compound symmetry.
 
The three-way interaction between visit & post-treatment visit indicator & treatment will be used to compare the change in slope in the treatment group to the change in slope in the placebo group.
 
The post-pre slope estimate for the active treatment group will be used to test the change from pre-transplantation to post-transplantation within the active treatment group.
 
Exploratory Objectives: The analysis for EIM (optional) and HHD will employ the same modeling approach as described above for the secondary objectives. The analysis for HHD will be based on a combined score reflecting muscles in the right arm.
 
A further analysis of HHD will compare the score for the right arm to the score for the left arm. The linear mixed model will include, in addition to the terms described above, an indicator for "right arm", interactions between that indicator and all other variables in the model, and a random effect term for the right arm indicator.
	

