6.5.3.5. Visit 5: Cell Transplantation (Days 0-2) 24-38 days from BMA

At the transplantation visit, subjects will be admitted to an inpatient study unit for study procedures. Pre-transplant activities will include:

- Review of concomitant medications
- Review of adverse events
- Vital sign measurements
- Directed physical examination including weight
- Neurological examination

- SVC pulmonary function test
- ALSFRS-R questionnaire
- Hand held dynamometry (HHD)
- Electrical impedance myography (EIM) will be collected only at centers that opt to participate in EIM data collection.
- Columbia Suicide Severity Rating Scale (C-SSRS) Since Last Visit

Following pre-transplant procedures, subjects will undergo intrathecal injection of cells or placebo as well as 24 intramuscular injections of cells or placebo (transplantation) along the biceps and triceps muscle of the right arm (If the physician is unable to inject into the right arm, the cells may be injected into the left arm and the fact recorded on the CRF. See Appendix 4, describing the procedure for the IM injections). CSF removed from the subject immediately prior to the intrathecal administration of cells will be retained for analysis.

Concomitant medications and adverse events will be monitored throughout the study visit, as necessary. In addition the following will be monitored:

- Vital signs will be monitored at hours 1, 2, 3, 4, 6, 16, 22, 28, 40, and upon discharge at 44 hours or up to 72 hours post transplantation. Inpatient observation is up to 72 hours, with earlier discharge at investigator discretion.
- Visual inspection of the injection sites will be performed at hours 1, 16 and 40.
- Directed physical examinations will be performed at hours 16, and 40 post-transplantation.
- Hematology, coagulation chemistry evaluations and biochemistries as well as urinalysis will be checked at 16 hours.
- Electrocardiogram (ECG) will be performed at 22 ± 4 hours post-transplantation

Prior to discharge, activities will include: vital signs, review of medications and adverse events and questionnaire for assessment of blinding.

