6.15.4.1. Product Handling and injection procedures

All syringes should be gently rotated for 20-30 seconds until all cells are in suspension.

For IM injections remove syringe cap and connect a 25Gx5/8" (0.5x16mm) needle.

[figure not shown]
With the needle in the upright position gently flick the syringe to surface any trapped bubbles. Push the plunger up until the first drop is visible at the tip of the needle. At this point the product is ready for injection.

6.15.4.2. Procedure:

1. For IM transplantation of MSC-NTF cells, the patient may be in a reclining or upright position. The upper arm area is prepped using aseptic technique. In case of a hairy arm the arm is shaved prior to IM injections.
2. The syringes for IM injection contain an 0.32 ml suspension of MSC-NTF cells, in a 1 ml Luer-Lock syringe (such as: Becton Dickinson Cat. No. 309628), attached to a 25Gx5/8" (0.5 x 16 mm, such as Becton Dickinson Cat. No. 300600) needle.
3. The MSC-NTF cell suspension (0.2 ml) is transplanted into the patient by multiple intramuscular injections (IM) to a 1.5 cm depth (ensuring that injection is into the muscle and not into adipose tissue) at 24 separate sites on the patient's right upper arm biceps and triceps muscles, according to a map based on the designed grid (see below).
4. The procedure is completed by withdrawing the needle.
5. The patient's arm is bandaged with a pressure bandage
6. The patient is typically asked to remain in the clinic area for at least 2 hours, and is monitored for signs of neurological problems.

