showing changes in suicide ideation scores from screening (lifetime measure) to worst on Baseline (pre-transplantation period) and from Baseline to worst post-treatment will also be provided. Data will be reported as available without data imputation.

12. Interim Analyses

There are no interim analyses planned for this study.

13. Deviations from Protocol-Stated Analyses

- [REDACTED]
- [REDACTED]
- [REDACTED]
- Updated mixed linear repeated measures statistical model to be a simple linear regression along with general linear model to compare changes in slopes between treatment groups as described above.
- Added slope analysis for 8-week and 16-week follow-up periods was added for the efficacy endpoints.
- Changed population definitions from the protocol stated definitions by removing analyses on mFAS and PP populations.
- Protocol referred to day of transplantation as Day 0, however in the SAP it is treated as Day 1.
- Changes between the original protocol and Amendment 1 are assumed to not impact any statistical analyses

14. Reporting Conventions

Reporting conventions will adhere when possible to the International Conference on Harmonization (ICH) Guidance E3, "Structure and Content of Clinical Study Reports". All tables and listings will be presented in landscape format. All SAS output for tables and listings will be distributed in PDF files.

15. References

16. SAP Revision History

Section #	Description of Change	Rationale
6	Updated FAS definition and removed mFAS	During the blinded data review it was determined that the difference between the FAS and mFAS was only one subject and hence no analyses would be performed on the mFAS

Section #	Description of Change	Rationale
6	Analysis on PP population is deleted	Due to the small sample size in the study, the 3:1 ratio of randomization between active and placebo and the possibility that a disproportionate number of the subjects may be in the Placebo group, analysis on the PP population will not be performed.
10.2 and 10.3.1	Updated the primary model from mixed-effects linear model to two-step model.	The mixed-effects linear model has restriction on the random effects estimates (slope) which causes the estimated slopes to be either lower or higher than the actual slopes from simple linear regression which was deemed to be more appropriate.

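### The protocol's exploratory HHD analyses are tied to the anatomical right arm although left-arm injection is allowed, so a left-injected patient's uninjected arm would be analysed as the injected one

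*Protocol*

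**What the plan says.** **Analysis.** Protocol 6.9.4.3, under Exploratory Objectives, defines the main HHD outcome by anatomical side: "The analysis for HHD will be based on a combined score reflecting muscles in the right arm". It then adds a side comparison: "A further analysis of HHD will compare the score for the right arm to the score for the left arm". The mixed model for that comparison gains a right-arm indicator, together with "interactions between that indicator and all other variables in the model, and a random effect term for the right arm indicator". The listed fixed effects end with site and the term that carries the side-specific treatment effect: "Four-way interaction between visit & post-treatment visit indicator & treatment & right arm indicator". The synopsis repeats the right-arm score and the right-arm indicator.

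**Injection.** The IM injections are unilateral and on the right by default (Protocol 6.3.3.3 and 6.6.4). Protocol 6.5.3.5 (Visit 5) makes an exception when the physician cannot inject the right arm: "the cells may be injected into the left arm and the fact recorded on the CRF". It then sends the reader on: "See Appendix 4, describing the procedure for the IM injections". Appendix 4 mentions only one side: "at 24 separate sites on the patient's right upper arm biceps and triceps muscles".

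**Measurement.** Protocol 6.9.3.1 has arm muscles examined on both sides.

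**SAP.** The HHD text is blacked out. The revision history (SAP Section 16) records, for Sections 10.2 and 10.3.1: "Updated the primary model from mixed-effects linear model to two-step model". Section 10.3.1 cannot be read.

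**The concern.** Cells or placebo go into the muscles of one arm only, and the documents give no other reason to single out the right arm. The right-versus-left model therefore serves as a within-patient comparison of the injected arm with the other arm, and the right-arm score serves as the injected-arm outcome. Both readings fail for a patient injected on the left.

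The protocol foresees such patients, yet no visible passage recodes the side, substitutes the injected arm or excludes them. Followed exactly, the stated rule enters their uninjected arm as the injected one. For an effect confined to the injected arm, a left-injected active patient then enters the side contrast with the opposite sign and adds nothing to the right-arm score.

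What is at stake is limited to the exploratory HHD results. The primary safety objective and the ALSFRS-R and SVC analyses do not depend on the arm.

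**Working it through.** The documents give no HHD effect size, variance or power, and Protocol 6.9.4.4 states that no formal sample size calculation was made. There is therefore no planned figure to reproduce. The size of the problem follows from the coding alone.

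**Inputs**
- Active patients: 36; placebo patients: 12 (protocol synopsis and 6.9.4.4).
- k: number of active patients injected on the left. Not given; assumed range 0 to 4, zero included.
- f: share of the injected-arm effect that is local to that arm. Not given; assumed range 0 to 1. The remainder, 1 − f, reaches both arms, for example from the intrathecal dose.
- Placebo injections are taken to have no local effect.

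**Right-minus-left contrast.** An effect common to both arms cancels within each patient. The local effect enters with sign + for the 36 − k right-injected patients and sign − for the k left-injected patients:

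(36 − k)/36 − k/36 = 1 − 2k/36

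**Right-arm score.** The common part is present in every active patient, and the local part only in the right-injected ones:

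(1 − f) + f(36 − k)/36 = 1 − f·k/36

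**Results** (fraction of the effect retained)

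| k | Contrast (of local effect) | Score, f = 1 | Score, f = 0.5 | Score, f = 0 |
|---|---|---|---|---|
| 0 | 1.000 | 1.000 | 1.000 | 1.000 |
| 1 | 0.944 | 0.972 | 0.986 | 1.000 |
| 2 | 0.889 | 0.944 | 0.972 | 1.000 |
| 4 | 0.778 | 0.889 | 0.944 | 1.000 |

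The contrast loses twice as much as the fully local score because each misassigned patient is reversed rather than merely set to zero.

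**Check on the model itself.** The fixed effects listed in Protocol 6.9.4.3 were fitted by least squares to noise-free data: 36 versus 12 patients, two arms, three sites, and HHD visits set at −14, −9, −5, 0, 2, 4, 8, 16 and 24 weeks. The four-way coefficient divided by the true local effect was 1.0000, 0.9444, 0.8889, 0.8333 and 0.7778 for k = 0 to 4, identical for f = 1 and f = 0.5. With f = 0 the coefficient was zero for every k. For the right-arm score with f = 1, the visit-by-post-by-treatment coefficient was 1.0000, 0.9722, 0.9444, 0.9167 and 0.8889 of the injected-arm effect. The fit agrees with the algebra.

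**With the arm defined by injection side**, every active patient enters with the correct sign, and both analyses keep the full effect for every k.

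**The case against.** The strongest objection is that the criticised text may no longer govern. The SAP moved from a mixed model to a two-step model, its HHD section cannot be read, and several entries in its list of deviations from the protocol are also blacked out. The SAP may already use the injected arm. This stands as a limit: the point can be made about the protocol wording only, and it says nothing certain about the analysis that will be run.

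Second, left injection is an exception and may never occur. This also stands, and at k = 0 there is no harm. But the protocol wrote the exception in, so its prespecified analysis should handle it. Otherwise the choice of arm is left until after the fact.

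Third, no sentence says that right stands for injected. This is an inference, but with one-sided injection on the right by default it is the only evident purpose of the side comparison.

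Fourth, recoding is not wholly neutral. The injected side is settled at Visit 5, after randomization at Visit 3, and a left-injected patient's comparison arm is the one that could not be injected. This is fair, and it is why a sensitivity analysis without these patients belongs with the recoding. Blinding reduces the risk that the choice of arm depends on treatment: Protocol 6.6.2 has active and placebo syringes masked. How well the blind holds is itself an exploratory question in Protocol 6.2.3.

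**Conclusion.** The concern holds for the protocol as a minor point. Protocol 6.9.4.3 and the synopsis apply a rule that is wrong for a case Protocol 6.5.3.5 allows. The loss is 2k/36 of a local effect in the side contrast and f·k/36 of the injected-arm effect in the right-arm score. For k between 1 and 4 that is 5.6% to 22.2% in the contrast and, for a fully local effect, 2.8% to 11.1% in the score. These figures rest on assumed values of k and f. The loss is nil if nobody is injected on the left. An effect shared by both arms is never misassigned: it is retained in the score and cancels from the contrast. Whether the SAP repeats the problem cannot be determined.

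**What to change.** 1. In the synopsis and Protocol 6.9.4.3, define the HHD score and the side variable by the injected arm, meaning the arm recorded on the CRF as receiving the IM injections, whether cells or placebo, in both groups. Call the other arm contralateral. Apply this to the score, the indicator, every interaction and the random effect.
2. Use the same definition in the SAP's HHD analysis, whichever model it uses, if it is not already there.
3. Add a sensitivity analysis that leaves out left-injected patients from both groups.
4. Reconcile two pairs of texts: Protocol 6.5.3.5 with Appendix 4 on the arm; and Protocol 6.9.3.1 with Appendix 2 on the arm tests. Protocol 6.9.3.1 lists elbow flexion and wrist extension, while Appendix 2 also describes shoulder flexion, elbow extension and first dorsal interosseous. The study manual cited in Protocol 6.5 may settle the second pair, but it is not among the documents.

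For the arm definition, the cost is a few wording changes and one derived variable. The injected side is on the CRF and both arms are measured, so no new data are needed. Recoding uses only the CRF side and does not reveal treatment. It should be dated before unblinding.
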